
 To evaluate the effect of continuing SZC as part of the discharge medications, compared to SoC, in reducing the total LOS in hospitalisations with HK as a contributing factor 	
 Continuous variable summary statistics (median and mean) of total LOS with HK as a contributing factor by randomised treatment group. Wilcoxon rank-sum test by randomised treatment group.

 To evaluate the effect of continuing SZC as part of the discharge medications, compared to SoC, in reducing the total LOS in all-cause hospitalisations 	
 Continuous variable summary statistics (median and mean) of total LOS in all-cause hospitalisations by randomised treatment group. Wilcoxon rank-sum test by randomised treatment group.

 To evaluate the effect of continuing SZC as part of discharge medications, compared to SoC in reducing the incidence of K-binder use 	
 Time to first occurrence of K-binder use in each arm at any time post-discharge up to 180 days.

 To evaluate the effect of continuing SZC as part of discharge medications, compared to SoC in reducing the frequency and duration of K-binder use 	
 Time to discontinuation of K-binder from initiation in each arm in the first instance of K-binder use post-discharge up to 180 days. Frequency of the use of K-binder to treat HK at any time post-discharge up to 180 days in each arm.

 To evaluate the effect of continuing SZC as part of the discharge medications, compared to SoC, in reducing the incidence of rescue therapy for HK use 	
 Time to first occurrence of rescue therapy use in each arm at any time post-discharge up to 180 days.

 To evaluate the effect of continuing SZC as part of the discharge medications, compared to SoC, in reducing the incidence of the composite outcome of all-cause hospitalisations, ED visits, or outpatient visits 	
 Time to first occurrence of all-cause hospitalisations, ED visits, or outpatient visits in each arm at any time post-discharge up to 180 days.

 To evaluate the effect of continuing SZC as part of the discharge medications, compared to SoC, in the change in eGFR 	
 Rate of change in (slope) eGFR from inpatient phase to 90 and 180 days post-discharge respectively, in each arm.

 To evaluate the effect of continuing SZC as part of the discharge medications, compared to SoC, in the incidence of dialysis initiation 	
 Time to first occurrence of dialysis initiation in each arm at any time post-discharge up to 180 days.

 To evaluate the effect of continuing SZC as part of the discharge medications, compared to SoC, in reducing the incidence of ICU admissions 	
 Time to first occurrence of ICU admissions in each arm at any time post-discharge up to 180 days.

• To evaluate the effect of continuing SZC as part of the discharge medications, compared to SoC, on the ability to continue RAASi	
• Descriptive summary of use of, and changes in use of, RAASi, at up to 90 and 180 days post-discharge, respectively, in each arm.
--	--

Abbreviations: AE = adverse event; ECG = electrocardiogram; ED = emergency department; eGFR = estimated glomerular filtration rate; HK = hyperkalaemia; HR = hazard ratio; ICU = intensive care unit; K⁺ = potassium; LOS = length of stay; NK = normokalaemia or normokalaemic; RAASi = renin-angiotensin-aldosterone system inhibitor; SoC = standard of care; SZC = sodium zirconium cyclosilicate.

4 STUDY DESIGN

4.1 Overall Design

- This is a Phase 4, randomised, controlled, open-label, parallel-group, multicentre study in participants with CKD treated for HK whilst in hospital.
- Participants from 30 to 50 sites in 4 to 7 countries will be screened for enrolment. Assuming a 20% drop out rate from enrolment to randomisation and a 20% drop out post-discharge (post-randomisation), approximately 163 participants will have to be enrolled to achieve 104 evaluable participants (52 per arm). In total, up to a maximum of 163 participants will be enrolled, resulting in approximately 130 participants discharged and randomised and 104 evaluable participants (52 per arm).
- The study plans to enrol approximately equal numbers of participants with mild HK (K^+ between > 5.0 and ≤ 5.5 mmol/L) and with moderate/severe HK (K^+ between > 5.5 and ≤ 6.5 mmol/L), with a minimum of 30% of the enrolled participants in either group.
- During the in-hospital phase, participants will be treated with SZC as per local label (correction and/or maintenance treatment, see Section 6.1), starting at baseline and based on local K^+ measurement obtained within 24 hours of treatment initiation:
 - Participants with HK (K^+ between > 5.0 and ≤ 6.5 mmol/L): 1) stop current K-binder if any, 2) start SZC correction dose (note: participants currently on SZC should continue SZC correction dose, up to 72 hours).
 - Participants currently receiving any treatment for the current episode of HK and are already NK at baseline ($K^+ \leq 5.0$ mmol/L): 1) stop any current K-binder, 2) start SZC maintenance dose (note: participants currently on SZC maintenance dose should continue SZC maintenance dose).
 - All treatment decisions, including modification of the ongoing therapy for HK, must be based on the investigator's medical judgement of the participant's best interest.
- At discharge, NK participants who have been treated with SZC for between 1 and 21 days whilst in hospital and are started on SZC maintenance dose will be randomised in a 1:1 ratio to one of the following arms:
 - Arm A: Participants discharged with SZC, as per local label, to manage HK until the end of the outpatient phase
 - Arm B: Participants discharged with SoC, as per local practice, to manage HK until the end of study.
- Note: Participants intended to be discharged with a K-binder (as per the site routine medical practice) will not be randomised and will be discontinued from the study. Still, participants randomised into Arm B may have a K-binder prescribed at Day 7 post-discharge (or after Day 7 post-discharge), to treat confirmed HK or in case there

is an increase in K⁺ level since discharge that, in the investigator's opinion, requires therapy.

- The total duration of the study for each participant will be up to approximately 6 months.
- Study visit schedule is as follows:
 - In-hospital phase:
 - The screening visit will occur while the participant is at the hospital (up to 21 days before discharge; medical monitor's approval may be sought for allowing longer duration hospital stays for specific participants) in order to check eligibility criteria
 - Inpatient phase:
 - The baseline visit (can occur the same day as the screening visit) where treatment with SZC will be initiated
 - The discharge visit, 1 to 20 days after baseline; medical monitor's approval may be sought for allowing longer duration hospital stays for specific participants). Randomisation will occur at day of discharge.
 - Outpatient phase:
 - Visits will occur at 7, 30, 60, 90, 120, 150, and 180 (EOT) days after randomisation. Only visits at 7, 90 and 180 days after randomisation will be on-site visits, the remaining being telephone visits. If dose titration occurs at any time during the outpatient phase, unscheduled dispensation visits will be performed.
 - Follow-up phase:
 - A follow-up on-site visit (end of study visit) will occur approximately 7 days after EOT.
- Data will be collected at on-site visits, via telephone visits and medical chart reviews.
- An adjudication committee will be involved in the study (see [Appendix A 5](#)).

4.2 Scientific Rationale for Study Design

Hospitalised CKD patients with HK are at higher risk of recurrent HK and of readmission than hospitalised CKD patients without HK.

CONTINUITY will recruit hospitalised participants with CKD (see inclusion criterion [#3](#) for details) and HK (see inclusion criterion [#4](#) for details). After treatment with SZC, the participants reaching NK will be randomised to either SZC or SoC treatment at discharge. The study aims to show that prescribing SZC as a part of the discharge medications in this population will result in an increased likelihood of maintained NK and a reduced incidence of all-cause hospital admissions or ED visits with HK as a contributing factor, compared with participants discharged with SoC.

The study interventions are SZC (as per local label) and SoC (as per local practice) groups. Participants in both groups will have K⁺ normalised at the beginning of the outpatient phase and monitoring of K⁺ will occur during study. Titration of SZC will be based on K⁺ values, according to Section 6.2 to ensure participants receive SZC at an individually optimised dose. Clear guidance is in place for rescue therapy for HK (see Section 6.7.1) as well as for study discontinuation (see Section 7).

The SoC as per local practice is used as comparator as there is currently no standardised therapy to treat patients with CKD and HK after discharge from the hospital.

The study is designed to align as much as possible with real-world clinical practice, with low number of mandated on-site follow-up visits (at Days 7, 90, and 180 post-discharge) and by using medical chart reviews and telephone contacts in between for complementary data collection.

CONTINUITY is a Phase 4 study, and as such it is designed to provide necessary and sufficient data to determine if there is an additional benefit of prescribing SZC at discharge in the selected population. The primary objective is to evaluate the efficacy of continuing SZC as part of the discharge medications, compared to SoC, in maintaining NK. The main secondary objective is to evaluate the effect of continuing SZC as part of the discharge medications, compared to SoC, in reducing the incidence of the composite outcome of all-cause hospital admissions or ED visits with HK as a contributing factor. Other secondary objectives include the outcome of hospital admissions with HK as a contributing factor. The definition of hospital admissions and ED visits *with HK as a contributing factor*, rather than *due to* HK, is based on the fact that HK is rarely determined as the primary cause of these health care encounters. An adjudication committee will be formed to determine whether HK was a contributing cause of the encounter. Note: This adjudication committee will also review the reported concomitant medications to determine RAASI down-titration/discontinuation events and use of rescue therapy for HK.

4.2.1 Participant Input into Design

Not applicable.

4.3 Justification for Dose

During both in-hospital and outpatient phases, SZC will be dosed according to its local label; see Sections 6.1 and 6.2.

Clinical studies in participants with HK consistently demonstrated that initial treatment with SZC 10 g three times daily (TID) for 24 hours up to 72 hours resulted in clinically meaningful K⁺ reduction with a majority of participants achieving NK within 24 to 48 hours. Moreover, participants with higher baseline K⁺ levels had greater reductions in K⁺ levels (Hoy, 2018).

Onset of efficacy was rapid with K^+ reduction observed as early as 1 hour after dose intake (Hoy, 2018).

After correction of HK, continued maintenance treatment for 28 days with SZC 5, 10, or 15 g daily resulted in continued effective control of K^+ within the NK range. The proportion of participants who remained NK at the EOT with SZC 5, 10, and 15 g daily increased dose-dependently (range: 71% to 85%) and was superior to placebo.

Long-term maintenance treatment with SZC for up to 12 months has also been studied. Once daily (QD) dosing with SZC, starting from 5 g QD and subsequently individualized, provided maintenance of NK for up to 12 months, with 87% of participants achieving $K^+ \leq 5.1$ mmol/L at Day 365 (Spinowitz et al, 2019).

4.4 End of Study Definition

A participant is considered to have completed the study if he/she has completed all phases of the study including the last scheduled procedure at visit 11, as shown in the Schedule of Activities (SoA; [Table 1](#)).

The end of the study is defined as the date of the last scheduled procedure shown in the SoA for the last participant in the study.

5 STUDY POPULATION

Prospective approval of protocol deviations to recruitment and enrolment criteria, also known as protocol waivers or exemptions, is not permitted. Rescreening of participants is allowed as detailed in Section [5.4](#).

The distribution of participants across the range of K^+ levels will be operationally controlled by ensuring that the following ratios are met:

- Approximately 50% enrolled participants with mild HK (K^+ between > 5.0 and ≤ 5.5 mmol/L) and approximately 50% with moderate/severe HK (K^+ between > 5.5 and ≤ 6.5 mmol/L)
- A minimum of 30% of enrolled participants in each group.

5.1 Inclusion Criteria

Participants are eligible to be included in the study only if all of the following criteria apply:

Age

- 1 Must be 18 years of age or older, at the time of signing the informed consent

Type of Participant and Disease Characteristics

- 2 Admitted to hospital (inpatient care; directly or from ED)
- 3 With:
 - Diagnosed CKD (any stage)
 - or
 - eGFR $< 90 \text{ mL/min/1.73 m}^2$ at, or within 3 months of, study screening, based on the Chronic Kidney Disease Epidemiology Collaboration (CKD-EPI) equation ([Levey et al, 2009](#)). Note: Race/ethnicity should not be included in CKD-EPI equation calculation.
- 4 Local laboratory K^+ measurement within 24 hours of baseline visit (visit 2), where result is either:
 - Hyperkalaemic as defined by site's local practice and $\text{K}^+ \leq 6.5 \text{ mmol/L}$
 - Or, normokalaemic: K^+ between ≥ 3.5 and $\leq 5.0 \text{ mmol/L}$, where patient started and is receiving treatment for this episode of HK.

Sex

- 5 Male or female

Informed Consent

- 6 Capable and willing of giving signed informed consent as described in [Appendix A](#) which includes compliance with the requirements and restrictions listed in the informed consent form (ICF) and in this protocol.

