- Participants currently receiving any treatment for the current episode of HK and are already NK at baseline ($\text{K}^+ \leq 5.0 \text{ mmol/L}$): 1) stop any

current K-binder, 2) start SZC maintenance dose (note: participants currently on SZC maintenance dose should continue SZC maintenance dose).

- All treatment decisions, including modification to the ongoing therapy for HK, must be based on the investigator's medical judgement of the participant's best interest.

Typically, NK is achieved within 24 to 48 hours. If participants are still hyperkalaemic after 48 hours of treatment, the same regimen can be continued for an additional 24 hours. If NK is not achieved after 72 hours of treatment, other treatment approaches should be considered, and the participant discontinued from the study.

Participants reaching NK (K^+ between 3.5 and 5.0 mmol/L, inclusive) within 72 hours will be started on maintenance dose of SZC until discharge.

Discharge visit: The day they get discharged from the hospital, participants will be randomised to one of the 2 parallel arms at this visit and enter the outpatient phase. To be randomised, participants have to be NK (K^+ between 3.5 and 5.0 mmol/L, inclusive) and should be started on a maintenance dose for SZC. The discharge visit will take place 1 to 21 days after the baseline visit. Medical monitor's approval may be sought for allowing longer duration hospital stays for specific participants.

- The outpatient phase:

Participants will be treated with either SZC, as per local label, or SoC, as per local practice for 180 days.

Visits will occur 7, 30, 60, 90, 120, 150, 180 (end of treatment [EOT]) days after discharge visit (randomisation). Only visits at 7, 90, and 180 days will be on-site visits: the remaining being telephone visits.

- The follow-up phase:

A follow-up site visit (end of study visit) will occur approximately 7 days after EOT.

Data will be collected at on-site visits, via telephone visits and medical chart reviews.

The study will be conducted in approximately 30 to 50 sites in 4 to 7 countries in Europe.

Disclosure Statement: This is a parallel-group treatment study with 2 treatment arms that are open label.

Masking: No masking

Number of Participants:

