9.4.3 Efficacy

9.4.3.1 Primary Endpoints

Occurrence (yes/no) of NK (K^+ between 3.5 and 5.0 mmol/L, inclusive) at 180 days post-discharge

- Population: FAS
- Endpoint: Occurrence (yes/no) of NK (K^+ between 3.5 and 5.0 mmol/L, inclusive) at 180 days post-discharge
- Intercurrent event strategy: Participants who discontinue treatment with a K^+ measurement at 180 days post-discharge will have this value used irrespective of treatment discontinuation (treatment policy strategy). Use of rescue therapy for HK will be considered to be non-response (composite variable strategy). The RAASI down-titration (including discontinuation) will be considered to be non-response (composite variable strategy). Participants who die of any cause prior to 180 days post-discharge or who are lost to follow-up for any reason will be considered to be non-response (composite variable strategy).
- Population level summary (analysis): Logistic regression analysis with response (occurrence) as the dependent variable and randomised treatment group as the

independent variable. The odds ratio along with the two-sided 95% confidence intervals and two-sided p-value (significance declared < 0.05) will be displayed.

Sensitivity Analyses

The analyses of the primary endpoint will be repeated by varying the estimand:

- Population level summary (analysis): Providing there are sufficient participants within each covariate to support the analysis, the logistic regression model will include randomised treatment group and the following baseline variables: age (as a spline), sex, presence of heart failure, diabetes, RAASi use, CKD stage, and baseline K⁺ (mild HK defined by K⁺ between > 5.0 and ≤ 5.5 mmol/L and moderate/severe HK defined by K⁺ between > 5.5 and ≤ 6.5 mmol/L) as independent variables.
- Intercurrent event strategy: As primary estimand, but participants needing rescue therapy for HK will follow the treatment policy strategy (ie, regardless of the intercurrent event).
- Intercurrent event strategy: As primary estimand, but participants with RAASi down-titration (including discontinuation) will follow the treatment policy strategy (ie, regardless of the intercurrent event).
- Intercurrent event strategy: As primary estimand but participants who die or are lost to follow-up prior to 180 days post-discharge will not be evaluated (completers analysis only).

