### **3.3.1.1 Screening / Baseline Period**

For all subjects, the screening period is defined as the period from informed consent to the first dose of SZC. For some variables, data from more than one assessment within the screening period may be collected prior to the first dose of SZC.

The baseline value for a variable is therefore defined as the last non-missing observation before the first dose of study treatment (SZC) in the inpatient period. For assessments on the day of first dose, where time is not captured, a nominal pre-dose indicator, if available, will serve as sufficient evidence that the assessment occurred prior to first dose. Any observation made after the first dose of study treatment will be considered post-baseline.

Assessments on the day of the first dose when neither time nor a nominal pre-dose indicator are captured will be considered prior to the first dose if such procedures are required by the protocol to be conducted before first dose.

In all quantitative summaries from baseline, absolute changes from baseline will be calculated as the post-baseline value minus the value at baseline. The percentage change from baseline will be calculated as  $[(\text{post-baseline value} - \text{baseline value}) / \text{baseline value}] \times 100$ .

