#### 4.2.2.5 Sensitivity Analyses of the Primary Endpoint

The analyses of the primary endpoint will be repeated as per section 4.2.2.4 but with alternative modelling:

- Population level summary (analysis): Providing there are sufficient participants within each covariate to support the analysis, the logistic regression model will include randomised treatment group and the following baseline variables: age (as a cubic spline), sex (male/female), participant recruitment country, presence of heart failure (yes/no), diabetes (yes/no), RAASi use (yes/no), CKD stage and baseline  $K^+$  ( $5.0 < K^+ \leq 5.5$  versus  $5.5 < K^+ \leq 6.5$  mmol/L) as independent variables. Sufficient participants for a covariate to be included will be considered if there are more than 10 participants with an event in each level of the covariate.

The analyses of the primary endpoint will be repeated as per section 4.2.2.4 but the estimand will be varied:

- Intercurrent event strategy: As primary estimand, but participants needing rescue therapy for HK will follow the treatment policy strategy (i.e., regardless of the intercurrent event).
- Intercurrent event strategy: As primary estimand, participants with RAASi down-titration (including discontinuation) will follow the treatment policy strategy (e.g. regardless of the intercurrent event).
- Intercurrent event strategy: As primary estimand, but participants who die or are lost to follow-up prior to 180 days post-discharge will not be evaluated (completers analysis only).
- Hypothetical strategy: As primary estimand, but participants who are lost to follow-up after 90 days (visit 7) or who are missing  $K^+$  status at 180 days will have their  $K^+$  status at 90 days, if available, carried forward to 180 days and included in the analysis using the principle of last observation carried forward.
- COVID-19 supplementary analysis: Intercurrent events not related to COVID-19 will be treated as per section 4.2.2.4. Participants who discontinue treatment due to COVID-19 will be treated as missing (hypothetical strategy). Use of rescue therapy for HK due to COVID-19 will be considered to be non-response (composite variable strategy). RAASi down-titration due to COVID-19 (including discontinuation) will be considered to be non-response (composite variable strategy). Participants who die due to COVID-19 will be treated as missing (hypothetical strategy).

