#### **4.2.3.5 Sensitivity Analyses of the Secondary Endpoint #1**

Providing there are sufficient events within each covariate ( $> 10$  events) to support the analysis, the analyses of time-to-event secondary endpoints will be repeated in the FAS using an alternative population level summary where the Cox proportional hazards model will include randomised treatment group and the following baseline variables: age (as a cubic spline), sex (female, male), participant recruitment country, presence of heart failure (yes/no), diabetes (yes/no), RAASi use (yes/no), CKD stage and baseline  $K^+$  ( $5.0 < K^+ \leq 5.5$  versus  $5.5 < K^+ \leq 6.5$  mmol/L) as independent variables.

Additionally, the analysis will be repeated with the PPS analysis population.

Furthermore, a supplementary analysis will be conducted where participants who down-titrated (or discontinue) RAASi will be censored at the date of down-titration.

An additional sensitivity analysis will be conducted where participants who are lost to follow-up will be accounted for using an inverse probability weighting (IPW) approach where similar participants who were not lost to follow-up will be re-weighted (hypothetical strategy). First, a logistic regression model will be performed where the dependent variable is a binary indicator variable where 1 indicates not lost to follow-up and 0 indicates lost to follow-up. Randomised treatment group and the following baseline variables: age (as a cubic spline), sex, participant recruitment country, presence of heart failure, diabetes, RAASi use, CKD stage and baseline  $K^+$  ( $5.0 < K^+ \leq 5.5$  versus  $5.5 < K^+ \leq 6.5$  mmol/L) will be included as independent variables. The predicted values from this model will be calculated and the reciprocal of these will be the IPW. The Cox proportional hazards model will then be conducted on participants not lost to follow-up, following the intercurrent event strategy in section 4.2.3.1, where participants will be reweighted using the IPW.

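### Participants normokalaemic at baseline fit no baseline K+ category, so under default fitting they fall out of the sensitivity, IPW, exploratory and subgroup analyses that use it

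*Protocol*

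**What the plan says.** **Eligibility.** Criterion 4 (Protocol 5.1) has two routes: hyperkalaemic up to 6.5 mmol/L, or K+ 3.5 to 5.0 "where patient started and is receiving treatment for this episode of HK". The second route is an expected group. Protocol 1.1 and 4.1 give separate instructions for "Participants currently receiving any treatment for the current episode of HK and are already NK at baseline", who start directly on maintenance SZC.

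**Baseline.** SAP 3.3.1.1 defines it as the "last non-missing observation before the first dose of study treatment (SZC) in the inpatient period".

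**Categories.** Protocol 9.4.3.1 specifies "baseline K⁺ (mild HK defined by K⁺ between > 5.0 and ≤ 5.5 mmol/L and moderate/severe HK" above 5.5 and up to 6.5. SAP 4.1.6.1 repeats these two bands. The subgroup sections add a three-band version that also begins above 5.0. No level, missing category or assignment rule covers 5.0 or below.

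**Use.** The adjusted Cox model in SAP 4.2.3.5 includes "diabetes (yes/no), RAASi use (yes/no), CKD stage and baseline" K+ in the two bands. The same section puts it in the weight model for loss to follow-up, where the listed variables "will be included as independent variables. The predicted values from this model will be calculated and the reciprocal of these will be the IPW".

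**Event rules.** SAP 4.2.2.5 sets this condition for the adjusted primary model: "Sufficient participants for a covariate to be included will be considered if there are more than 10 participants with an event in each level". SAP 4.2.3.5 asks for more than 10 events for the adjusted Cox model, and the subgroups need 10 or more events per category.

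**Enrolment.** Protocol 5 plans about 50% with mild HK and "approximately 50% with moderate/severe HK", with at least 30% in each.

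**The concern.** Followed as written, the eligibility criterion and the baseline definition produce K+ values that fit no level of a named model term. Most software then deletes the participant from the fit. The deletion is not random: these participants had already responded to HK treatment before the first study dose. A covariate-adjusted sensitivity analysis would then change the population and the adjustment together, and a difference from the FAS result could not be put down to either one.

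The IPW analysis is the most exposed. It is meant to correct for selection through loss to follow-up, yet an unclassified participant gets no predicted probability and so no weight, which adds a second selection.

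**Working it through.** **1. The plan's own figure.** The sample size for the main secondary endpoint (Protocol 9.2.2) reproduces.
- Hazard ratio: ln(0.83)/ln(0.568) = 0.329.
- Events by Freedman's formula, two-sided 5%, 80% power: (1.960 + 0.842)² × (1.329/0.671)² = 30.8, so 31.
- Mean event proportion: (0.17 + 0.432)/2 = 0.301. 31/0.301 = 103, so 52 per arm.
- Enrolment: 104/0.8 = 130 randomised; 130/0.8 = 162.5, so 163.

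Nothing here challenges that calculation. It supplies the expected events: 0.301 × 104 = 31.3 if only evaluable participants contribute, 0.301 × 130 = 39.1 if all randomised do.

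**2. Which analyses contain the K+ term.**

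| Analysis | SAP section | K+ term | Sufficiency rule |
|---|---|---|---|
| Main primary logistic | 4.2.2.4 | no | – |
| Main secondary log-rank, Cox, negative binomial | 4.2.3.4, 4.2.5.4 and cross-references | no | – |
| Main K+ and eGFR mixed models | 4.2.13.4, 4.2.22.4 | no | – |
| Adjusted logistic | 4.2.2.5 | yes | yes |
| Adjusted Cox | 4.2.3.5 and cross-references | yes | yes |
| Adjusted negative binomial | 4.2.5.5, 4.2.14.5 | yes | yes, no number given |
| Adjusted K+ mixed model | 4.2.13.5 | yes | yes, no number given |
| IPW | 4.2.3.5 and cross-references | yes | none |
| Adjusted Cox, exploratory 10, 12, 13, 15, 16 | 4.2.18.5, 4.2.20.5, 4.2.21.5, 4.2.23.5, 4.2.24.5 | yes | none |
| K+ subgroups | 4.2.2.6 and 4.2.3.7 to 4.2.8.7 | yes | 10 events per category |

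Of the nine sensitivity analyses of the primary endpoint in 4.2.2.5, one uses baseline K+. Of the four for secondary endpoint #1 in 4.2.3.5, two do (adjusted Cox and IPW).

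**3. Size.** The documents do not give the normokalaemic share. I assume 10–40%. The upper end follows from the two 30% floors, if they are met on baseline K+: 100 − 2 × 30 = 40% of enrolled. The lower end is illustrative. I also assume the same share among randomised participants and the same event rate in this group.

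| Share | Unclassified of 130 | Left | Main secondary events lost (of 31.3 / 39.1) | Events left (of 31.3 / 39.1) |
|---|---|---|---|---|
| 10% | 13 | 117 | 3.1 / 3.9 | 28.2 / 35.2 |
| 20% | 26 | 104 | 6.3 / 7.8 | 25.0 / 31.3 |
| 30% | 39 | 91 | 9.4 / 11.7 | 21.9 / 27.4 |
| 40% | 52 | 78 | 12.5 / 15.7 | 18.8 / 23.5 |

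More than 10 events in each of two levels needs at least 22. On the 104 basis that becomes impossible above a share of 1 − 22/31.3 = 30%; on the 130 basis it remains possible throughout the range.

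**4. Would a separate ≤5.0 level meet the rules?** At 10–20% it would hold about 3 to 8 main secondary events, too few for either event rule. For the primary endpoint, planned responders are 65 × 0.88 + 65 × 0.59 = 95.6; at 10% the level would hold 9.6, just short of more than 10.

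**The case against.** The best defence is that the band was always meant to come from the qualifying hyperkalaemic value. The enrolment targets of about 50% and 50% add to 100%, which fits only if normokalaemic entrants are placed by their episode K+. Footnote i to the Schedule of Activities lets routine-care K+ serve for screening and requires it to lie above 5.0 and up to 6.5. The footnote to SAP Table 1 admits K+ recorded before consent. This is a fair reading of intent. But the Table 1 footnote only assigns values to Visit 1, and SAP 3.3.1.1 still takes the last pre-dose value, so a later normokalaemic result replaces the qualifying one. The written rule leaves the gap open.

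Three further points stand and limit the concern.
- Exclusion is inferred from complete-case defaults; the SAP does not state it.
- The sufficiency rules may keep K+ out of an adjusted model or stop the model from running. They do not cover the IPW analysis or the five exploratory Cox models.
- The K+ subgroups exist to describe mild against moderate/severe HK. A participant in neither band does not bias either estimate; the bands simply do not add up to the FAS.

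A reader might infer that every adjusted analysis loses these participants, or that the sensitivity analyses as a set cannot test the FAS result. The documents do not support that. The main logistic and Cox models adjust for country only, and eight of the nine primary sensitivity analyses have no K+ term.

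**Conclusion.** The gap is real and internal to the documents: eligible, randomised participants can have a baseline K+ that fits no category. It affects only the analyses that contain the K+ term. The primary test, the hierarchy in SAP 3.3.4 and the main secondary analyses are not touched.

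Under the assumed 10–40% share, 13–52 of about 130 randomised participants are unclassified. The figure of about 3–16 events out of 31–39 applies to the main secondary endpoint alone and should not be carried to other endpoints, which have different event totals or, for the mixed models, no events. The size rests on the assumed share, on equal event rates and on complete-case deletion. That the categories omit these participants rests on none of these. The plan should be corrected, but its confirmatory conclusions do not depend on it.

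**What to change.** In SAP 4.1.6.1, define the K+ band for covariate, IPW and subgroup use from the qualifying hyperkalaemic value of the index episode, and say which recorded value that is. Leave the upper band open above 5.5: the normokalaemic route in criterion 4 puts no ceiling on the earlier value of the episode, so a limit of 6.5 could reopen the gap. Where the value is unavailable, use a ≤5.0 on-treatment level or enter baseline K+ as a continuous term, and state how any participant still unclassified is handled. Refer to this definition from every section that uses the bands.

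The cost is a short text change, which Protocol 9.4 allows before database lock, and a check that the qualifying value was recorded for normokalaemic entrants; the documents do not confirm that it was. A separate third level costs one degree of freedom and, if sparse, may fail the covariate rule or the subgroup rule, so banding on the qualifying value is preferable. A continuous term avoids sparse levels but puts on-treatment and untreated K+ values on one scale.
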